## 8.2. Safety Analyses

The safety analyses will be based on the All Treated Subjects population, unless otherwise specified.

Table 5, Table 6, and Table 7 provide overviews of the planned analyses, with further details of data displays being presented in Appendix 14: List of Data Displays.

## 8.2.1. Overview of Planned Adverse Events Analyses

All AEs will be categorized by the MedDRA (version 20.0 or higher if available) system organ class and preferred term to tabulate the number and incidence.

AEs of special interest will be manually-selected at patient-level (i.e. following case-bycase review by members of the SRT including representatives from the local Japan team) and not at preferred term level.

Endpoint / Parameter/ Display Type		Absolu		
	Sun	nmary	Individual	
	Т	F	L	
Adverse Events (AEs)				
On-therapy AEs by SOC and PT	Y		Y	
On-therapy AEs by SOC and PT	v			
by Dialysis Status	1			
On-therapy AEs by SOC and PT and Maximum Intensity	Y			
On-therapy AEs up to Week 4 by SOC and PT	Y			
On-therapy AEs up to Week 4 by SOC and PT	V			
by Dialysis Status	T			
On-therapy AEs up to Week 4 by SOC and PT and Maximum Intensity	Y			
Post-therapy AEs by SOC and PT	Y		Y	
Post-therapy AEs by SOC and PT and Maximum Intensity	Y			
On-therapy Drug-Related AEs by SOC and PT	Y			
On-therapy Drug-Related AEs by SOC and PT	V			
by Dialysis Status	T			
On-therapy Drug-Related AEs by SOC and PT and Maximum Intensity	Y			
On-therapy Drug-Related AEs up to Week 4 by SOC and PT	Y			
On-therapy Drug-Related AEs up to Week 4 by SOC and PT	V			
by Dialysis Status	T			
On-therapy Drug-Related AEs up to Week 4 by SOC and PT and Maximum	v			
Intensity	1			
Post-therapy Drug-Related AEs by SOC and PT	Y			
Post-therapy Drug-Related AEs by SOC and PT and Maximum Intensity	Y			
On-therapy Common (>= 5 %) Non-Serious AEs by SOC and PT (Subjects & No. of Occurrences)	Y			

#### Table 5 Overview of Planned AEs Analyses

Endpoint / Parameter/ Display Type		Absolute		
	Sum	nmary	Individual	
	Т	F	L	
Subject Numbers for Individual AEs			Y	
Relationship Between AE SOCs, PT & Verbatim Text			Y	
Serious and Other Significant AEs			-	
Fatal Serious AEs			Y	
Non-Fatal Serious AEs			Y	
On-therapy Serious AEs	Y			
Post-therapy Serious AEs	Y			
Serious AEs in Screening Period [1]			Y	
Reasons for Considering as a Serious AE			Y	
Serious AEs by SOC and PT (Subjects & No. of Occurrences)	Y			
AEs Leading to Withdrawal from Study / Permanent Discontinuation of Study	v		v	
Treatment by SOC and PT			I	
CV Events			Y	
AEs of special interest [2]				
On-therapy AEs of special interest	Y		Y	
On-therapy AEs of special interest	v			
by Dialysis Status	1			
Post-therapy AEs of special interest	Y		Y	
Other Safety Summary for Plain Language Summary				
On-therapy Serious Drug-Related AEs	Y			
On-therapy Non-Serious Drug-Related AEs	Y			

NOTES:

- T = Table, F = Figures, L = Listings, Y = Yes display generated, SOC = System Organ Class, PT = Preferred Term.
- Summary = Represents TF related to any summaries (i.e. descriptive statistics) of the observed raw data.

• Individual = Represents FL related to any displays of individual subject observed raw data.

[1] Listing will be based on All Screening Population.

[2] See Section 10.6.4.

#### 8.2.1.1. Planed AE Analyses Displays

#### • Adverse Events

#### AEs by SOC and PT

The number and percentage of subjects reporting at least one AE will be provided. These events will be summarized by primary system organ class and preferred term. On-therapy, on-therapy up to week 4, and post-therapy AEs will be summarized separately. On-therapy AE will be also summarized by baseline dialysis status.

#### AEs by SOC and PT and Maximum Intensity

AEs will be summarized by Maximum Intensity (not applicable, mild, moderate, or severe) by primary system organ class and preferred term. Subjects who experience the same event several times with different intensities will only be counted with the maximum intensity in the order of (not applicable < mild < moderate < severe). On-therapy, on-therapy up to week 4, and post-therapy AEs will be summarized separately.

#### Drug-Related AEs by SOC and PT

The number and percentage of subjects reporting at least one drug-related AE will be provided. These events will be summarized by primary system organ class and preferred term. On-therapy, on-therapy up to week 4, and post-therapy AEs will be summarized separately. On-therapy AE will be also summarized by baseline dialysis status.

#### Drug-Related AEs by SOC and PT and Maximum Intensity

Drug-related AEs will be summarized by Maximum Intensity (not applicable, mild, moderate, or severe) by primary system organ class and preferred term. Subjects who experience the same event several times with different intensities will only be counted with the maximum intensity in the order of (not applicable < mild < moderate < severe). On-therapy, on-therapy up to week 4, and post-therapy AEs will be summarized separately.

#### On-therapy Common (>= 5 %) Non-Serious AEs by SOC and PT (Subjects & No. of Occurrences)

The number and percentage of subjects reporting at least one on-therapy common ( $\geq 5$  %) non-serious AE will be provided. The number of on-therapy non-serious AE occurrences will also be provided. These events will be summarized by primary system organ class and preferred term.

#### • Serious and Other Significant AEs

#### Serious AEs

The number and percentage of subjects reporting at least one Serious AE will be provided. These events will be summarized by primary system organ class and preferred term. Onand post-therapy serious AEs will be summarized separately.

#### On-therapy Serious AEs by SOC and PT (Subjects & No. of Occurrences)

The number and percentage of subjects reporting at least one on-therapy serious AE will be provided. The number of on-therapy serious AE occurrences will also be provided. These events will be summarized by preferred term.

#### AEs Leading to Withdrawal from Study / Permanent Discontinuation of Study Treatment by SOC and PT

The number and percentage of subjects reporting each on-therapy AE leading to discontinuation of study treatment will be summarized. These events will be summarized by preferred term.

### • AEs of Special Interest (AESIs)

How to identify the AESIs is described in Section 10.6.4.

#### AEs of Special Interest

The number and percentage of subjects reporting at least one AESI will be provided. These events will be summarized by each AESI term (See Section 10.6.4). On-therapy and post-therapy AESIs will be summarized separately. On-therapy AE will be also summarized by baseline dialysis status.

#### • Other Safety Summary for Plain Language Summary

#### Serious/Non-serious Drug-Related AEs

The number and percentage of subjects with on-therapy serious or non-serious drugrelated AEs will be summarized by preferred term. The serious AEs and the non-serious AEs will be summarized separately.

## 8.2.2. Overview of Planned Clinical Laboratory Analyses

#### Table 6Overview of Planned Clinical Laboratory Analyses

Endpoint / Parameter/ Display Type		Absolute			Change from BL		
	Sum	Summary Individual		y Individual Summary		Individual	
	Т	F	L	Т	F	L	
Chemistry							
Chemistry Values by Visit	Y		Y	Y			
Percent change from Baseline in Lipid Parameters [1] (total cholesterol, LDL cholesterol, and HDL cholesterol)			Y	Y	Y		
Worst Case Chemistry Results Relative to Normal Range Post-Baseline Relative to Baseline	Y						
Worst Case Chemistry Results Relative to PCI Criteria Post-Baseline Relative to Baseline	Y						
Hematology							
Hematology Values by Visit	Y		Y	Y			
Worst Case Hematology Results Relative to Normal Range Post-Baseline Relative to Baseline	Y						
Worst Case Hematology Results Relative to PCI Criteria Post-Baseline Relative to Baseline	Y						
Other Laboratory Tests [2]							

Endpoint / Parameter/ Display Type	Absolute			Change from BL			
	Summary		Individual	Summary		Individual	
	Т	F	L	Т	F	L	
Other Laboratory Values by Visit [2]	Y		Y	Y			
Worst Case Other Laboratory Results Relative to Normal Range Post-Baseline Relative to Baseline [2]	Y						
Worst Case Other Laboratory Results Relative to PCI Criteria Post-Baseline Relative to Baseline [2]							
Hepatobiliary (Liver)							
Liver Monitoring/Stopping Event Reporting	Y						
Hepatobiliary Laboratory Abnormalities	Y						
Medical Conditions for Subjects with Liver Stopping Events			Y				
Substance Use for Subjects with Liver Stopping Events			Y				
Scatter Plot of Maximum vs. Baseline for ALT		Y[3]					
Scatter Plot of Maximum ALT vs Maximum Total Bilirubin		Y 					
All Laboratory							
All Laboratory Data for Subjects with any Value of Potential Clinical Concern/PCI			Y				
Laboratory Values of PCI			Y				

NOTES:

• T = Table, F = Figures, L = Listings, Y = Yes display generated, PCI = Potential Clinical Importance

• Summary = Represents TFL related to any summaries (i.e. descriptive statistics) of the observed raw data.

• Individual = Represents FL related to any displays of individual subject observed raw data.

[1] Lipid parameters will be log-transformed and the percent change from baseline will be reported.

[2] Only iPTH will be collected as other laboratory tests.

[3] This figure may not be provided in this study because this is required for 'larger study' by the GSK Core RAP requirements in the RAP Template.

#### 8.2.2.1. Planned Clinical Laboratory Analyses Displays

#### • Chemistry/Hematology/Other Laboratory Tests

#### Clinical Laboratory Values by Visit

The values will be summarized using mean, standard deviation, median, minimum, and maximum at each assessment visit and baseline. Chemistry values, hematology values, and other laboratory values will be summarized separately.

#### Percent change from Baseline in Lipid Parameters

Lipid parameters will be log-transformed and the percent change from baseline will be reported. The percent change from baseline in each lipid parameter, including baseline values, will be summarized using geometric mean, 95% CI, minimum, median, and maximum at each assessment visit. In baseline values, the coefficient of variation will also be provided.

## Clinical Laboratory Changes from Baseline by Visit

The values will be summarized using mean, standard deviation, median, minimum, and maximum at each assessment visit. Change from baseline in chemistry, hematology, and other laboratory will be summarized separately.

### *Worst Case Laboratory Results Relative to Normal Range/PCI Criteria Post-Baseline Relative to Baseline*

The number of subjects with worst laboratory results relative to normal range/potential clinical importance (PCI) criteria which are post-baseline relative to baseline, including unscheduled assessments, will be summarized by test and category. Summaries for normal range and PCI will be provided separately. The categories for normal range are: To Low, To Normal or No Change, To High; the categories for PCI criteria are: To Low, To w/in Range or No Change, To High. The categorization is determined by comparing the baseline category to the worst case post-baseline category.

### • Hepatobiliary (Liver)

Details of liver chemistry stopping criteria are described in the protocol.

Liver monitoring/stopping events will be summarized.

Hepatobiliary laboratory abnormalities will be summarized.

A scatter plot of maximum on-therapy ALT values versus baseline ALT values will be produced if larger data permit.

A scatter plot of maximum total bilirubin (xULN) versus maximum ALT (xULN) values on-therapy will be produced if larger data permit.

## 8.2.3. Overview of Planned Other Safety Analyses

#### Table 7 Overview of Planned Other Safety Analyses

Endpoint / Parameter/ Display Type	Absolute			Change from BL					
	Summary		Individual	Summary		Individual			
	Т	F	L	Т	F	L			
ECG									
ECG Findings by Visit	Y		Y						
ECG Values by Visit			Y	Y					
Abnormal ECG Findings			Y						
Vital Signs									
Vital Signs by Visit	Y		Y	Y					
Worst Case Vital Sign Results Relative to PCI Criteria Post-Baseline Relative to Baseline	Y								

Endpoint / Parameter/ Display Type	Absolute			Change from BL					
	Summary		Individual	Summary		Individual			
	Т	F	L	Т	F	L			
All Vital Signs for Subjects with Values of PCI			Y						
Ophthalmology									
Ophthalmologic Exams at Screening	Y		Y						
On-Therapy Ophthalmologic Exams	Y		Y						

NOTES:

- T = Table, F = Figures, L = Listings, Y = Yes display generated, PCI = Potential Clinical Importance
- Summary = Represents TFL related to any summaries (i.e. descriptive statistics) of the observed raw data.
- Individual = Represents FL related to any displays of individual subject observed raw data.

#### 8.2.3.1. Planned Other Safety Analyses Displays

#### • *ECG*

ECG findings ('normal', 'abnormal, not clinically significant', 'abnormal, clinically significant') will be summarized by each assessment visit. Findings without regard to visits (labelled "Worst Case Post-Baseline", only the worst case finding for each subject, will also be provided. All ECG measures (heart rate, PR interval, QRS duration, QT (uncorrected) interval and QTcB (calculated), result of ECG) will be included in a subject listing.

#### • Vital Signs

Vital sign values will be summarized using mean, standard deviation, minimum, median, and maximum for each assessment visit. Separate summary statistics of pre- and postdialysis vital signs will be provided for raw values and change from baseline. In a summary of change from baseline, each baseline value (i.e. pre- and post-dialysis baseline) will be used for calculation (Section 10.5.2).

The number of subjects with worst case vital sign results relative to PCI criteria which are post-baseline relative to baseline, including unscheduled assessments, will also be summarized by test and category. The categories for PCI criteria are: To Low, To w/in Range or No Change, To High. The categorization is determined by comparing the baseline category to the worst case post-baseline category.

#### • Ophthalmology Exams

The responses to each question will be summarized using number and percentage at each assessment visit. The response will be classified into 'Yes' and 'No'. Ophthalmology exam at screening and at on-therapy will be summarized separately. The number of subjects with worst case after-screening ophthalmology exams (i.e., the response is 'Yes' at least once during whole treatment period, including unscheduled visits) will also be summarized by each question.

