7.4.2. Adverse Events of Special Interest

The investigator (or subinvestigator) or designee will be responsible for detecting, documenting, and reporting any AEs of special interest listed below. These events have been identified based on the known safety profiles of ESAs, theoretical or potential risks based on the mechanism of action of GSK1278863, and findings from completed nonclinical studies of GSK1278863.

- Thrombosis and/or tissue ischemia secondary to excessive erythropoiesis
- Death, myocardial infarction (MI), stroke, heart failure, thromboembolic events, thrombosis of vascular access
- Cardiomyopathy
- Pulmonary artery hypertension
- Cancer-related mortality and tumor progression and recurrence
- Esophageal and gastric erosions
- Proliferative retinopathy, macular edema, choroidal neovascularization
- Exacerbation of rheumatoid arthritis

Any relevant AE should be recorded in the relevant section of the subject's eCRF.

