3.38.	All Treated Subjects	LIVER1	Summary of Liver Monitoring/Stopping Event Reporting	IDSL	Y		
3.39.	All Treated Subjects	LIVER10	Summary of Subjects Meeting Emergent Hepatobiliary Laboratory Abnormality Criteria	IDSL Listing may be sufficient if few events.	Y		
ECG				-			
3.40.	All Treated Subjects	EG1	Summary of ECG Findings	IDSL	Y		
3.41.	All Treated Subjects	EG2	Summary of Change from Baseline in ECG Values by Visit	IDSL	Y		
Vital S	igns						
3.42.	All Treated Subjects	SAFE_T3 based on VS1	Summary of Vital Signs by Visit	Summarized by each assessment status (i.e. pre-dialysis and post-dialysis)	Y		
3.43.	All Treated Subjects	SAFE_T3 based on VS1	Summary Change from Baseline in Vital Signs by Visit	Summarized by each assessment status (i.e. pre-dialysis and post-dialysis)	Y		
3.44.	All Treated Subjects	SAFE_T4 based on VS7	Summary of Worst Case Vital Sign Results Relative to PCI Criteria Post-Baseline Relative to Baseline	Summarized by each assessment status (i.e. pre-dialysis and post-dialysis)	Y		
Ophth	Ophthalmology						

Safety	Safety : Tables							
No.	Populatio n	IDSL / TST ID / Example Shell	Title	Programming Notes	SAC			
3.45.	All Treated Subjects	SAFE_T5	Summary of Ophthalmologic Exams at Screening		Y			
3.46.	All Treated Subjects	SAFE_T6	Summary of On-Therapy Ophthalmologic Exams		Y			
Safety	Summaries f	or a Plain Langua	ge Summary					
3.47.	All Treated Subjects	AE3	Summary of On-Therapy Serious Drug-Related AEs		Y			
3.48.	All Treated Subjects	AE3	Summary of On-Therapy Non-Serious Drug-Related AEs		Y			

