No.	Population	IDSL / TST ID / Example Shell	Title	Programming Notes	SAC		
49.	All Treated Subjects	LIVER5	Listing of Liver Monitoring/Stopping Event Reporting		Y		
50.	All Treated Subjects	LIVER6	Listing of Liver Stopping Event Information for RUCAM Score		Y		
51.	All Treated Subjects	LIVER7	Listing of Liver Biopsy Details		Y		
52.	All Treated Subjects	LIVER8	Listing of Liver Imaging Details		Y		
53.	All Treated Subjects	EG3	Listing of ECG Values		Y		
54.	All Treated Subjects	EG5	Listing of ECG Findings		Y		
55.	All Treated Subjects	VS4	Listing of Vital Signs		Y		
56.	All Treated Subjects	VS4	Listing of All Vital Signs for Subjects with Values of PCI		Y		
57.	All Treated Subjects	SAFE_L2	Listing of Ophthalmologic Exams		Y		
Pharm	acokinetic Para	ameters					
58.	PK	PK07	Listing of GSK1278863 Pharmacokinetic Concentration-Time Data by Dose level		Y		
59.	PK	PK13	Listing of Derived GSK1278863 Pharmacokinetic Parameters by Dose level		Y		

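### The worst-case ophthalmology row ignores the screening answer, so it can mix pre-existing with new eye findings

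*SAP*

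**What the plan says.** SAP 8.2.3.1 (Ophthalmology Exams) reduces each exam question to a Yes/No answer, summarised by visit. It states that "Ophthalmology exam at screening and at on-therapy will be summarized separately". It then adds a worst-case after-screening count for each question, where a subject is included if "the response is 'Yes' at least once during whole treatment period, including unscheduled visits". The list of displays (SAP 10.14.6) has Table 3.45 for screening and Table 3.46, "Summary of On-Therapy Ophthalmologic Exams". No shift or cross-tabulation is listed. Subject-level data appear in Listing 57, "Listing of Ophthalmologic Exams".

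The laboratory worst-case tables follow a different rule: "The categorization is determined by comparing the baseline category to the worst case post-baseline category". The vital-sign worst-case table uses the same baseline-relative rule.

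Ophthalmology assessments are a protocol safety endpoint (Protocol Section 3). In Protocol Appendix 2 the exams are listed as mitigation for the risk that Section 7.4.2 names as an AESI: "Proliferative retinopathy, macular edema, choroidal neovascularization".

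**The concern.** The study has one arm, so a subject's own screening exam is the only reference for judging whether an eye finding is new. Pre-existing eye disease can enter the study: the exclusion criteria (Protocol 5.2) name no eye condition, and footnote 11 to Protocol Table 6 allows for findings at the screening exam. If a stable finding is answered Yes at screening and Yes again on treatment, it is counted in the worst-case row exactly as a new finding would be. A reader of Table 3.46 could take the row as an on-treatment incidence when part or all of it was present before the first dose. The opposite error is also possible: new findings can be masked when some screening findings resolve and the totals stay level.

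**Working it through.** The documents give no count or rate for eye findings, so there is no stated figure to reproduce on this point. What can be checked is how much the two planned totals reveal about new findings.

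**Inputs.** N = 22 enrolled (Protocol 9.2.1), assumed all treated, each with a screening exam and at least one on-therapy exam. All counts and probabilities below are illustrative assumptions.

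**Step 1: bounds from the two totals.** For one question, let S be the number Yes at screening (Table 3.45) and W the number with a worst-case Yes (Table 3.46). New findings (No then Yes) plus persistent findings (Yes then Yes) equal W. Persistent findings cannot exceed S, and new findings cannot exceed N − S. So

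max(0, W − S) ≤ new findings ≤ min(W, N − S).

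- S = 5, W = 5: max(0, 0) = 0 to min(5, 17) = 5.
- S = 6, W = 6: 0 to min(6, 16) = 6.
- S = 6, W = 8: 2 to min(8, 16) = 8.

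**Step 2: two patterns that produce the same two totals (S = 5, W = 5).**

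| Pattern | Persistent | Resolved | New | S | W | New among No at screening |
|---|---|---|---|---|---|---|
| A | 5 | 0 | 0 | 5 | 5 | 0/17 |
| B | 3 | 2 | 2 | 5 | 5 | 2/17 (11.8%) |

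Both give a worst-case row of 5/22 (23%) beside a screening row of 5/22. The resolved findings matter. With 3 persistent, 2 new and none resolved, Table 3.45 would show 3, and the pair 3 and 5 would reveal at least 2 new findings.

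**Step 3: expected size of the mixing.** Let p be the share Yes at screening, r the probability that such a subject is Yes again on treatment, and q the probability of a new Yes in a subject who was No. The worst-case row expects N[pr + (1 − p)q] subjects, of whom N(1 − p)q are new.

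| Assumption | Worst-case row, p = 0.1 to 0.4 | Of which new |
|---|---|---|
| q = 0, r = 1 | 2.2 to 8.8 (10% to 40%) | 0 |
| q = 0, r = 0.8 | 1.8 to 7.0 (8% to 32%) | 0 |
| q = 0.05, r = 1 | 3.2 to 9.5 (15% to 43%) | 1.0 to 0.7 |

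**Step 4: denominator.** Only subjects who were No at screening can have a new finding. In Pattern A that is 22 − 5 = 17 subjects (the match with the protocol's 17 expected completers is a coincidence). The exact two-sided 95% upper limit for 0/n is 1 − 0.025^(1/n): 19.5% for 0/17. Using 0/22 would give 15.4% and overstate the precision.

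**The case against.** **A reader might infer that pre-existing eye findings are being reported as AESIs.** The documents do not support that. Table 3.46 summarises exam responses. AESIs are selected by case-by-case patient-level review of adverse events (SAP 8.2.1 and 10.6.4) and reported in Tables 3.22 to 3.24. Adverse events are collected from the start of treatment (Protocol 7.4.1.1), and fluctuations of a pre-existing condition that does not worsen are not adverse events (Protocol 12.6.1). Protocol 7.4.7 says the exams serve the assessment of ocular adverse events, so new or worsened disease has its own reporting route. This objection stands in full.

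**The question wording is not available.** The mock shells are held separately (SAP Appendix 15), and Tables 3.45 and 3.46 use different shells. If the on-therapy form asks only about new or worsened findings, the problem largely disappears. This makes the point conditional but does not remove it: SAP 8.2.3.1 states no such restriction, and different shells are explained by the visit and worst-case rows that only the on-therapy table needs.

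**Eye exams are not the only exception.** The ECG worst-case summary, in which "only the worst case finding for each subject, will also be provided", also takes no account of baseline. The inconsistency is therefore with laboratory tests and vital signs, not with every safety domain. ECG values do, however, have a change-from-baseline table (3.41); the eye exams have no baseline-relative display at all.

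**With about 22 subjects, Listing 57 lets a reader pair answers by hand**, and the SAP's amendment log presents the worst-case row as an additional way of summarising. Both are true. But the row exists to summarise, and a listing does not correct a summary that can be misread.

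**Conclusion.** The point holds in a limited, conditional form. As written, the worst-case row takes no account of the screening answer, and separate screening and on-therapy totals cannot in general identify new findings: 5 and 5 out of 22 leave anything from 0 to 5 possible. This rests on one assumption that the documents do not settle, namely that a stable pre-existing finding is answered Yes again on treatment. The sponsor can settle it by checking the form. The counts are illustrative; no prevalence of eye findings is given.

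The effect is on the interpretation of one descriptive safety row. It does not extend to the AESI tables, the primary endpoint or the sample size. The screening data are not hidden either: they have their own table and appear in the listing.

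**What to change.** First check the exam form. If every on-therapy question is restricted to new or worsened findings, say so in SAP 8.2.3.1; no further change is needed.

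Otherwise, in Table 3.46, for each question asked both at screening and on therapy:

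- Cross-tabulate the screening response by the worst on-therapy response: No–No, No–Yes, Yes–No, Yes–Yes.
- Report n (%) with a new finding among subjects who were No at screening, with that group as denominator.
- Add a footnote that the Yes–Yes cell may hide worsening of an existing finding, and refer to Listing 57 and the ocular adverse events for those subjects.

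The responses are already collected, so the cost is minor programming and a revised table shell.
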